 12. Return to normal function at 30 minutes postdose will be assessed using the percentage of subjects with a functional disability level of normal at 30 minutes postdose in the subset of subjects with functional disability at the time of dosing.
 13. Pain relief at 15 minutes postdose will be assessed using the percentage of subjects with a pain intensity of none or mild at 15 minutes postdose.
 14. Return to normal function at 15 minutes postdose will be assessed using the percentage of subjects with a functional disability level of normal at 15 minutes postdose in the subset of subjects with any level of functional disability at the time of dosing.
 15. Rescue medication use within 24 hours postdose will be assessed using the percentage of subjects who take rescue medication within 24 hours after taking study drug.
 16. Nausea freedom at 2 hours postdose will be assessed using the percentage of subjects with nausea absent at 2 hours postdose in the subset of subjects with nausea present at the time of dosing.
 17. Pain relapse from 2 to 48 hours postdose will be assessed using the percentage of subjects with a pain intensity of mild, moderate, or severe at any time point after 2 hours through 48 hours postdose in the subset of subjects with pain freedom at 2 hours postdose.
-

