9.3.1 Efficacy Analyses

The intercurrent event of rescue medication use will be handled using RM=F, i.e., subjects who take rescue medication will be classified as failures for all efficacy assessments that are reported at or after taking rescue medication. The RM=F method will apply to all efficacy endpoints, except the secondary efficacy endpoint of rescue medication use within 24 hours postdose.

9.3.1.1 *Primary Endpoints*

Zavegepant will be tested for superiority against placebo at an $\alpha=0.05$ level for both co-primary endpoints using the efficacy analysis set. For each endpoint, treatment groups will be compared using a Cochran-Mantel Haenszel test to estimate the difference in percentages of subjects achieving the endpoint response criteria (zavegepant – placebo) stratified by prophylactic migraine medication use at randomization (yes or no). The percentage of subjects achieving the endpoint response criteria will be presented with a 95% confidence interval (CI) by treatment group. The difference in percentages between treatment groups will be presented with a 95% CI and p-value.

Subjects with missing data at 2 hours postdose will be classified as failures (i.e., Non-Completer = Failure; NC=F).

Sensitivity analyses will be described in the SAP.

9.3.1.2 *Secondary Endpoints*

If the tests of both co-primary endpoints are significant (i.e., both p-values are ≤ 0.05), then the secondary endpoints will be tested hierarchically at the $\alpha=0.05$ level in the order shown in the Secondary Endpoints section, using the efficacy analysis set. Thus, a secondary endpoint will be tested only if the preceding secondary endpoint in the hierarchy is determined to be significant (i.e., p-value ≤ 0.05). The same statistics will be presented as those for the co-primary endpoints.

For endpoints based on a single time point, such as phonophobia freedom at 2 hours postdose, subjects with missing data at a single time point will also be classified as failures. For endpoints based on multiple time points, such as sustained pain relief from 2 to 48 hours postdose, subjects with missing data at (1) 2, 24, or 48 hours postdose, or (2) more than 1 time point from 3 to 8 hours postdose will also be classified as failures.

9.3.2 *Safety Analyses*

Deaths will be listed without regard to onset for the enrolled analysis set.

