6.3.1.1 Overall Summary of Primary and Secondary Endpoints

An overall summary of treatment comparisons of all primary and secondary endpoints tested hierarchically presents the following statistics:

- Response rate (i.e., “n/N” and percentage) and 95% CI for each treatment group
- Stratified percentage difference between treatment groups (zavegepant – placebo), 95% CI, and p-value.

Analyses are based on main methods described in Sections 6.3.2 and 6.3.3. Endpoints are displayed in the order presented in Sections 3.1.1 and 3.1.2. P-values that are determined to be significant based on the testing hierarchy are identified.

A forest plot of treatment comparisons of all primary and secondary endpoints tested hierarchically is produced for zavegepant versus placebo based on the overall summary. The plot displays the following statistics:

- Response rate (i.e., “n/N” and percentage) by treatment group

- Stratified percentage difference between treatment groups (zavegepant – placebo) and 95% CI.

Percentage differences with p-values that are determined to be significant based on the testing hierarchy are identified. Note that the plot displays results for *no* rescue medication use within 24 hours postdose and *no* pain relapse from 2 to 48 hours postdose so that positive percentage differences favor zavegepant for these secondary endpoints.

6.3.1.2 *Missing Efficacy Data*

Missing efficacy data are tabulated by treatment group as the number and percentage of subjects in the efficacy analysis set in the following categories:

- Missing pain intensity at each time point from 15 minutes through 48 hours postdose. These categories are not mutually exclusive because subjects may have missing pain intensity at multiple time points.
- Number of time points with missing pain intensity from 2 hours to 48 hours postdose: 0 (i.e., no missing pain intensity), 1, 2, 3, 4, 5, 6, 7. These categories are mutually exclusive.
- Missing data for the following efficacy parameters at 2, 24, and 48 hours postdose: pain intensity, nausea status, phonophobia status, photophobia status, and functional disability level.

In addition, missing pain intensity at 2 hours postdose are tabulated by subgroup level for each treatment group and overall for all subgroups specified in Section 4.3 plus the following subgroups:

- Pain intensity at the time of dosing (moderate or severe)
- MBS on study before dosing (nausea, phonophobia, or photophobia)
- Rescue medication use: yes, no.

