6.3.3.6 Sustained Pain Freedom From 2 to 48 Hours Postdose

Sustained pain freedom from 2 to 48 hours postdose is defined as pain intensity of none at all time points from 2 to 48 hours postdose.

Subjects who meet all of the following criteria are classified as responders:

- Pain intensity of none at all time points from 2 to 48 hours postdose, i.e., in the 2 to 48-hour postdose analysis windows

- Missing pain intensity at ≤ 1 time point from 3 to 8 hours postdose, i.e., in the 3, 4, 6, or 8-hour postdose analysis windows
- No rescue medication taken at or before 48 hours postdose (see Section 6.3.3.4).

Subjects who are not classified as responders and have any of the following are classified as failures:

- Rescue medication taken at or before 48 hours postdose (RM=F; see Section 6.3.3.4)
- Mild, moderate or severe pain at any time point from 2 to 48 hours postdose, i.e., in the 2, 3, 4, 6, 8, 24, or 48-hour postdose analysis window
- Missing pain intensity at 2, 24, or 48 hours postdose (NC=F), i.e., in the 2, 24, or 48-hour postdose analysis window
- Missing pain intensity at > 1 time point from 3 to 8 hours postdose (NC1=F), i.e., in the 3, 4, 6, or 8-hour postdose analysis window.

Sustained pain freedom from 2 to 48 hours outcomes are tabulated for the efficacy analysis set by treatment group as the number and percentage of subjects in the following categories:

- Responder: (1) Pain intensity of none at all time points from 2 to 48 hours postdose, (2) missing pain intensity at ≤ 1 time point from 3 to 8 hours postdose, and (3) no rescue medication taken at or before 48 hours postdose
- Failure
 - Rescue medication taken at or before 48 hours postdose (RM=F)
 - Mild, moderate, or severe pain intensity at any time point from 2 to 48 hours postdose
 - Severe pain intensity
 - Moderate pain intensity
 - Mild pain intensity
 - Missing pain intensity at 2, 24, or 48 hours postdose (NC=F)
 - Missing pain intensity at > 1 time point from 3 to 8 hours postdose (NC1=F).

Failure subcategories are mutually exclusive, because subjects who meet more than 1 failure criterion are classified according to the first failure criterion met; in case of ties, the first failure subcategory that is met in the hierarchy above is chosen.

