Treatment group comparisons of the percentage of subjects with sustained pain freedom from 2 to 48 hours postdose use analogous methods as the main analysis of the co-primary endpoint of pain freedom with NC=F, NC1=F, and RM=F (see Section 6.3.2.1).

6.3.3.7 *Freedom from Photophobia, Phonophobia or Nausea at 2 Hours Postdose*

Freedom from each symptom (nausea, phonophobia, photophobia) at 2 hours postdose is assessed separately. Symptom status is measured as present or absent for each symptom (nausea, phonophobia, photophobia).

Symptom freedom at a single time point postdose is defined as a symptom absent at that time point for subjects with the symptom present at the time of dosing. Thus, all analyses of symptom freedom are based on the efficacy analysis set with the symptom present at the time of dosing (see Section 7.5.2), e.g., nausea freedom at a single time point postdose are based on subjects with nausea present at the time of dosing.

Symptom freedom outcomes at 2 hours postdose are tabulated by treatment group (see Section 6.3.4.1).

Treatment group comparisons of the percentage of subjects with symptom freedom at 2 hours postdose use analogous methods as the main analysis of the co-primary endpoint of pain freedom with NC=F and RM=F (see Section 6.3.2.1).

6.3.3.8 *Rescue Medication Use within 24 Hours Postdose*

Analyses are based on the evaluable efficacy analysis set, i.e., subjects in the efficacy analysis set with rescue medication start date on or before study drug start date + 1 day and missing rescue medication start time are excluded. Time to rescue medication use is measured from the study drug start date/time to the rescue medication start date/time.

No analysis window around the 24-hour postdose time point is used.

Rescue Medication Use within 24 Hours Postdose

Rescue medication use within 24 hours postdose is defined as time to rescue medication use ≤ 24 hours.

Treatment group comparisons of the percentage of subjects using rescue medication within 24 hours postdose use analogous methods as the main analysis of the co-primary endpoint of pain freedom, except that the NC=F and RM=F methods are not applied because they are not applicable to this endpoint (see Section 6.3.2.1).

Time to Rescue Medication Use through 24 Hours Postdose

Time to rescue medication use through 24 hours postdose is assessed by treatment group as follows:

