- Kaplan-Meier plot and table using 2-hour time intervals (i.e., 0 to 2, > 2 to 4, ... , > 24). The Kaplan-Meier plot displays the percentage of subjects taking rescue medication within 24 hours postdose on the y-axis versus time in hours on the x-axis.

- Time-to-event distribution table (hours), including a log-rank p-value (zavegepant versus placebo).

See Section 6.1.1.1 for time-to-event plot and table attributes. Rescue medication use through 24-hours postdose is considered as an event in these time-to-event analyses. Subjects who do not take rescue medication within 24 hours postdose are censored at 24 hours and 1 minute (i.e., 1441 minutes).

6.3.3.9 *Pain Relapse from 2 to 48 Hours Postdose*

Pain relapse from 2 to 48 hours postdose is defined as pain intensity of mild, moderate, or severe at any time point postdose after 2 hours postdose for subjects with pain intensity of none at 2 hours postdose. Thus, analyses of pain relapse are based on the efficacy analysis set with pain freedom at 2 hours postdose (see Section 6.3.2.1).

Subjects who meet all of the following criteria are classified as non-relapsers:

- Pain intensity of none at all time points after 2 hours postdose, i.e., in the 3 to 48-hour postdose analysis windows
- Missing pain intensity at ≤ 1 time point after 2 hours postdose, i.e., in the 3, 4, 6, 8, 24, or 48-hour postdose analysis window
- No rescue medication taken at or before 48 hours postdose (see Section 6.3.3.4).

Subjects who have any of the following are classified as relapsers:

- Rescue medication taken at or before 48 hours postdose (RM=F; see Section 6.3.3.4)
- Mild, moderate, or severe pain intensity at any time point after 2 hours postdose, i.e., in the 3, 4, 6, 8, 24, or 48-hour postdose analysis window
- Missing pain intensity at > 1 time point after 2 hours postdose (NC1=F), i.e., in the 3, 4, 6, 8, 24, or 48-hour postdose analysis window.

Pain relapse from 2 to 48 hours outcomes are tabulated by treatment group as the number and percentage of subjects in the following categories:

- Non-relapser: (1) Pain intensity of none at all time points after 2 hours postdose, (2) missing pain intensity at ≤ 1 time point after 2 hours postdose, and (3) no rescue medication taken at or before 48 hours postdose
- Relapser
 - Rescue medication taken at or before 48 hours postdose (RM=F)
 - Mild, moderate, or severe pain intensity at any time point after 2 hours postdose
 - Severe pain intensity
 - Moderate pain intensity

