 - Mild pain intensity

- Missing pain intensity at > 1 time point after 2 hours postdose (NC1=F).

Relapser subcategories are mutually exclusive, because subjects who meet more than 1 relapse criterion are classified according to the first relapse criterion met; in case of ties, the first relapse subcategory that is met in the hierarchy above is chosen.

Treatment group comparisons of the percentage of subjects with pain relapse from 2 to 48 hours postdose use analogous methods as the main analysis of the co-primary endpoint of pain freedom with NC1=F and RM=F (see Section 6.3.2.1).

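### Pain relapse 2–48 hours: the SAP lets a subject with only the 24- or 48-hour score missing count as a non-relapser, where the protocol makes that missing score a failure

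*SAP*

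**What the plan says.** Protocol 9.3.1.2 gives one missing-data rule for secondary endpoints that span several assessments. Its scope is "For endpoints based on multiple time points, such as sustained pain relief from 2 to 48 hours postdose", and those classified as failures are "subjects with missing data at (1) 2, 24, or 48 hours postdose, or (2) more than 1 time point from 3 to 8 hours" after dosing. Protocol 3.2 defines pain relapse, among subjects pain-free at 2 hours, as "pain intensity of mild, moderate, or severe at any time point after 2 hours through 48 hours postdose". That makes it a multi-time-point endpoint, and the protocol states no exception for it.

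The SAP carries this rule into the four sustained endpoints (6.3.3.3 to 6.3.3.6). For sustained pain freedom 2–48 hours the failure criteria include "Missing pain intensity at 2, 24, or 48 hours postdose (NC=F), i.e., in the 2, 24, or 48-hour postdose analysis window". The one-missing allowance covers only the 3-, 4-, 6- and 8-hour windows, and the comparison uses the methods of the "co-primary endpoint of pain freedom with NC=F, NC1=F, and RM=F (see Section 6.3.2.1").

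For pain relapse (SAP 6.3.3.9) the text differs. A non-relapser may have one missing score anywhere among 3, 4, 6, 8, 24 and 48 hours. The missing-data route to relapser needs more than one missing "time point after 2 hours postdose (NC1=F), i.e., in the 3, 4, 6, 8, 24, or 48-hour postdose analysis window". The methods sentence refers to the "co-primary endpoint of pain freedom with NC1=F and RM=F (see Section 6.3.2.1"), so NC=F is no longer listed. No reason is given for treating this endpoint differently.

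**The concern.** The SAP changes a classification rule that the protocol states outright, for an endpoint that is formally tested at alpha 0.05 if the hierarchy reaches it.

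The two late scores matter more than the early ones. From 3 to 8 hours the scores are 1 to 2 hours apart, so neighbouring scores bracket a single gap. If the 48-hour score is missing, no pain score exists after the 24-hour window closes at 25 hours. If the 24-hour score is missing, none exists from 8 hours 15 minutes to 47 hours. Only the rescue record covers those stretches, yet the subject is reported as free of relapse through 48 hours.

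Two reported results will also fail to reconcile. Non-relapsers will outnumber sustained pain-free 2–48 hour responders by the number of subjects in these patterns, and the relapse outcome table has no row that shows them.

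**Working it through.** **1. Compare the rules pattern by pattern.** Take a subject who is pain-free at 2 hours, has every observed later score equal to none, and took no rescue. Each of the six later scores (3, 4, 6, 8, 24, 48 hours) is observed or missing: 2^6 = 64 patterns.

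| Rule | Patterns giving non-relapser | Count |
|---|---|---|
| Protocol 9.3.1.2 | none missing (1), or exactly one of 3, 4, 6, 8 h missing (4) | 5 |
| SAP 6.3.3.9 | none missing (1), or exactly one of all six missing (6) | 7 |

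The rules disagree in 7 − 5 = 2 patterns: only 24 hours missing, and only 48 hours missing. They agree in the other 62, and no pattern differs in the opposite direction.

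**2. Number of subjects at planning rates.** Protocol 9.1 and SAP 5 give 630 evaluable per group and pain freedom at 2 hours of 22.8% and 15.5%. These inputs reproduce the stated power: 91.0% for pain freedom (stated 91%), 87.6% for MBS freedom (88%) and 79.6% jointly (80%), with a two-sided two-proportion test at 0.05 and the product for the joint figure.

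- Zavegepant: 0.228 × 630 = 143.6
- Placebo: 0.155 × 630 = 97.7
- Total pain-free at 2 hours: 241.3

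**3. Effect on the reported relapse rate.** The documents give no missingness rate, so what follows uses assumed values. Let m be the share of these subjects whose only missing score is the 24- or the 48-hour one, r′ the share of that group with pain or rescue recorded elsewhere (relapsers under both rules), and r the relapse rate in everyone else.

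- SAP rate = r(1 − m) + m·r′
- Protocol rate = r(1 − m) + m
- Difference = m(1 − r′)

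| m | r′ = 0 (upper bound) | r′ = 40% | r′ = 60% |
|---|---|---|---|
| 5% | 5.0 points (12.1 subjects) | 3.0 (7.2) | 2.0 (4.8) |
| 10% | 10.0 points (24.1 subjects) | 6.0 (14.5) | 4.0 (9.7) |

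To relate m to missingness per assessment, suppose each of the six scores is missing independently with probability q. Then m = 2q(1 − q)^5:

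| q | m | Zavegepant subjects | Placebo subjects |
|---|---|---|---|
| 1% | 1.9% | 2.7 | 1.9 |
| 3% | 5.2% | 7.4 | 5.0 |
| 5% | 7.7% | 11.1 | 7.6 |
| 10% | 11.8% | 17.0 | 11.5 |

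These counts are upper bounds, because they take r′ = 0.

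**4. Effect on the treatment difference.** It is zero if m and r′ are equal in both arms. If m is 10% in one arm and 5% in the other, the two rules give differences that are (0.10 − 0.05)(1 − r′) apart: 5 points at r′ = 0, 3 at 40%, 2 at 60%. For scale, with 40% relapse assumed in both arms, the standard error is sqrt[0.4 × 0.6 × (1/144 + 1/98)] = 6.4 points.

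**The case against.** The strongest defence is that SAP 6.3 defines NC=F for single-time-point endpoints and NC1=F, over a specified period, as the main method for multi-time-point endpoints. On that reading 6.3.3.9 applies a stated method with 3 to 48 hours as its period. This explains how the text may have arisen but does not resolve the conflict. The general definition leaves the period open, the SAP sets it to 3–8 hours for every other multi-time-point secondary endpoint, and the protocol states the rule itself. Protocol 9.3 does refer to the SAP for full details, but detail is not licence to change a stated rule.

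A second point is that the protocol says failure and never says that failure means relapser. That is an inference, but the only workable one: the SAP itself sends both RM=F and NC1=F to relapser.

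Third, the size is assumed and could be small. This stands. At 1% missing per assessment, fewer than 5 subjects in total are involved. In the earlier study 1,578 of 1,588 treated subjects completed (Protocol 1.3.2), though that is study completion, not diary completion.

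Fourth, the subjects can be traced in the by-subject listings of SAP 6.3.1 and 6.3.2. That is true, but no table shows them. In SAP 6.3.1.2, "Missing efficacy data are tabulated by treatment group as the number and percentage of subjects in the efficacy analysis set", which is not the 2-hour pain-free subset.

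Finally, neither rule is free of bias under unequal missingness: the SAP rule favours the arm with more of it, and the protocol rule penalises that arm. This also stands. The case for the protocol rule is that it was prespecified and matches the sustained endpoints, not that it is unbiased.

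**Conclusion.** The concern holds. SAP 6.3.3.9 contradicts Protocol 9.3.1.2 for exactly two missing-data patterns, and a subject in either one, with no pain or rescue recorded elsewhere, is classified inconsistently between sustained pain freedom 2–48 hours and pain relapse. That conclusion rests on the text alone.

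The size rests on assumptions. With 5–10% of 2-hour pain-free subjects in these patterns, the SAP rule lowers reported relapse by 2 to 10 points; with 1% missing per assessment, by at most 1.9 points. The treatment difference moves only if the patterns are unequally common, or differ in recorded relapse or rescue, between arms: by 2 to 5 points under an assumed 10% versus 5%, less than one standard error.

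The reach is limited. Relapse is the 17th and last secondary endpoint, so the co-primary results, the other secondary tests and the power are untouched. It is still a tested endpoint and should follow the protocol rule.

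**What to change.** Before unblinding, amend SAP 6.3.3.9 as follows:

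1. Add a relapser criterion, and a matching outcome category, for a missing pain score at 24 or 48 hours, labelled NC=F.
2. Limit the one-missing allowance to the 3-, 4-, 6- and 8-hour windows, in both the non-relapser and the NC1=F criteria and categories.
3. Add NC=F to the methods sentence.
4. Keep the present rule as a sensitivity analysis.
5. Add a programming check that non-relapsers equal sustained pain-free 2–48 hour responders in each arm. Under the protocol rule the two counts must match.

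A clause in SAP 6.3 saying that multi-time-point endpoints also apply NC=F at the 24- and 48-hour scores they include would bring the general definitions into line with 6.3.3.3 to 6.3.3.6 as well.

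The cost is a few lines of SAP text and one table shell. The derivation already exists for sustained pain freedom 2–48 hours. Reported relapse rates will be higher by the share of subjects in the two patterns who have no recorded pain or rescue.

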6.3.4 Exploratory Efficacy Endpoints

All exploratory efficacy endpoints are evaluated for the efficacy analysis set, unless specified otherwise.

Any p-values presented for exploratory efficacy endpoints are for descriptive purposes only, and not included in the hierarchical testing.

6.3.4.1 Efficacy Outcomes over Time: Main Analyses

Efficacy outcomes are tabulated for the efficacy analysis set by treatment group as the number and percentage of subjects in categories (responder; failure; failure subcategories) at each time point from 15 minutes through 48 hours postdose. Subjects who are not classified as responders at a time point are classified as failures. Failure subcategories are mutually exclusive, because subjects who meet more than 1 failure criterion are classified according to the first failure criterion met; in case of ties, the first failure subcategory that is met in the specified hierarchy for an endpoint is chosen. Percentages for response rates are also shown with exact Clopper-Pearson 95% CIs.

Outcomes are presented separately for each of the following efficacy endpoints: pain freedom, MBS freedom, pain relief, nausea freedom, phonophobia freedom, photophobia freedom, and return to normal function. These analyses use the NC=F and RM=F methods to align with main analyses of co-primary and secondary endpoints (see Sections 6.3.2 and 6.3.3). Outcomes category nomenclature is as follows:

- “at time point” means in the analysis window of that postdose time point
- “No rescue medication taken at or before time point” means either (1) rescue medication start date/time missing, or (2) rescue medication start date/time $> \{eDiary \text{ finding date/time for the data assessment in the analysis window of that postdose time point}\}$
- “Rescue medication taken at or before time point” means either (1) rescue medication start date/time $\leq \{eDiary \text{ finding date/time for the data in the analysis window of that postdose time point}\}$, or (2) (rescue medication start date/time – study drug start date/time) \leq upper bound of the analysis window corresponding to that postdose time point (see Section 7.3), if the data are missing in the time point analysis window.

Outcomes for the efficacy analysis set are presented over time as described below. Subjects who are excluded from analyses have the following outcomes in by-subject listings:

- Subjects in the randomized analysis set who are not in the efficacy analysis set: “Not in the efficacy analysis set”
- Subjects in the efficacy analysis set with normal or missing functional disability level at the time of dosing for return to normal function: “Not evaluable: normal function at the time of dosing” or “Not evaluable: missing disability level at the time of dosing”
- Subjects in the efficacy analysis set with absent or missing symptom status at the time of dosing for photophobia freedom, photophobia freedom, and nausea freedom: “Not evaluable: symptom absent at the time of dosing” or “Not evaluable: symptom missing at the time of dosing”.

Pain Freedom Outcomes over Time

Outcomes categories are defined as:

- Responder: Pain intensity of none at time point and no rescue medication taken at or before time point
- Failure
 - Rescue medication taken at or before time point (RM=F)
 - Mild, moderate, or severe pain intensity at time point
 - Severe pain intensity
 - Moderate pain intensity
 - Mild pain intensity
 - Missing pain intensity at time point (NC=F).

Pain Relief Outcomes over Time

Outcome categories are defined as:

- Responder: Pain intensity of none or mild at time point and no rescue medication taken at or before time point
- Failure
 - Rescue medication taken at or before time point (RM=F)
 - Moderate or severe pain intensity at time point
 - Severe pain intensity
 - Moderate pain intensity
 - Missing pain intensity at time point (NC=F).

MBS Freedom Outcomes over Time

Outcome categories are:

- Responder: MBS reported on study before dosing that is absent at time point, and no rescue medication taken at or before time point
- Failure
 - Missing MBS on study before dosing
 - Rescue medication taken at or before time point (RM=F)
 - Nausea reported as MBS on study before dosing and present at time point
 - Phonophobia reported as MBS on study before dosing and present at time point
 - Photophobia reported as MBS on study before dosing and present at time point
 - Missing MBS status at time point (NC=F).

Return to Normal Function Outcomes over Time

Analyses are based on the efficacy analysis set with functional disability at the time of dosing (see Section 7.5.2).

Outcomes categories are defined as:

- Responder: functional disability level of normal at time point and no rescue medication taken at or before time point
- Failure
 - Rescue medication taken at or before time point (RM=F)
 - Functional disability at time point
 - Requires bedrest
 - Moderately impaired
 - Mildly impaired
 - Missing functional disability level at time point (NC=F).

Phonophobia Freedom, Photophobia Freedom, and Nausea Freedom Outcomes over Time

Freedom from each symptom (phonophobia, photophobia, and nausea) is evaluated separately. Analyses are based on the efficacy analysis set with the symptom present at the time of dosing (see Section 7.5.2).

Outcomes categories are defined as:

- Responder: symptom absent at time point and no rescue medication taken at or before time point
- Failure
 - Rescue medication taken at or before time point (RM=F)
 - Symptom present at time point
 - Missing symptom status at time point (NC=F).

6.3.4.2 *Complete Cases over Time: Sensitivity Analyses*

Response rates corresponding to efficacy outcomes over time are also presented using complete cases for each of the following efficacy endpoints: pain freedom, pain relief, MBS freedom, return to normal function, phonophobia freedom, photophobia freedom, and nausea freedom. Percentages for response rates are also shown with exact Clopper-Pearson 95% CIs.

In these sensitivity analyses, subjects who are missing data in a postdose time point analysis window are excluded at that time point (NC=M). Results for the co-primary endpoints of pain freedom and MBS freedom at 2 hours postdose are the same as those for the complete cases sensitivity analyses (see Sections 6.3.2.1 and 6.3.2.2).

For MBS freedom, the following conventions are applied: (1) first, subjects whose MBS reported on study before dosing is missing are classified as failures; (2) next, the RM=F method of handling rescue medication use is applied; (3) finally, subjects with missing MBS status in the analysis window are excluded.

For all other endpoints, the RM=F method of handling rescue medication use is applied first, and then subjects with missing data in the analysis window are excluded.

6.3.4.3 *Time-to-event Efficacy Endpoints*

The following time-to-event endpoints are analyzed:

- Pain freedom through 4 hours postdose
- Pain freedom through 8 hours postdose
- Pain relief through 4 hours postdose
- Pain relief through 8 hours postdose
- MBS freedom through 8 hours postdose for subjects with MBS reported on study before dosing
- Return to normal function through 8 hours postdose for subjects with functional disability at the time of dosing

- Phonophobia freedom through 8 hours postdose for subjects with phonophobia present at the time of dosing
- Photophobia freedom through 8 hours postdose for subjects with photophobia present at the time of dosing
- Nausea freedom through 8 hours postdose for subjects with nausea present at the time of dosing.

Analyses are based on non-missing, postdose efficacy data relevant to each endpoint.

For a given time-to-event endpoint, subjects are considered to have an event through X hours ($X = 4$ or 8) if the first postdose eDiary finding date/time defining response is (1) at or before the upper bound of the X -hour analysis window in minutes (see Table 5), and (2) is before the imputed rescue medication start date/time, if not missing (see Section 7.1).

Otherwise, subjects who do not have an event through X hours are censored at the earliest of the following: (1) upper bound of the X -hour analysis window + 1 minute; (2) time from the study drug start date/time to the imputed rescue medication start date/time, if the time is at or before the upper bound of the X -hour analysis window in minutes; (3) time from the study drug start date/time to the last non-missing finding date/time defining the endpoint, if the time was before the lower bound of X -hour analysis window in minutes.

For each endpoint listed above, time to event is assessed by treatment group as follows:

- Kaplan-Meier plot and table using the following time intervals postdose: 0 to 15, >15 to 30, > 30 to 45, > 45 to 60, > 60 to 90, > 90 to 120, > 120 to 180, > 180 to 240, > 240 to 360, > 360 to 495, and > 495 minutes. The Kaplan-Meier plot displays the percentage of subjects with the event on the y-axis versus time in minutes on the x-axis.
- Time-to-event distribution table (minutes), including a log-rank p-value (zavegepant versus placebo).

See Section 6.1.1.1 for additional table and plot attributes.

6.3.4.4 *Efficacy Endpoints Compared over Time*

Treatment group comparisons of the percentage of subjects achieving response over time use analogous methods as the main analysis of the co-primary endpoint of pain freedom with NC=F and RM=F (see Section 6.3.2.1) for the efficacy analysis set and the following endpoints:

- Pain freedom
- Pain relief
- MBS freedom
- Return to normal function for subjects with functional disability at the time of dosing
- Phonophobia freedom for subjects with phonophobia present at the time of dosing
- Photophobia freedom for subjects with photophobia present at the time of dosing

- Nausea freedom for subjects with nausea present at the time of dosing.

For each endpoint and time point from 15 minutes through 48 hours postdose, the following are presented:

- Response rate (i.e., “n/N” and percentage), ASE, and 95% CI for each treatment group
- Stratified percentage difference between treatment groups (zavegepant – placebo), ASE, 95% CI, and p-value.

Response at each time point is defined in Section 6.3.4.1. Note that some of these analyses overlap with those of primary and secondary efficacy endpoints in Sections 6.3.2 and 6.3.3.

